5 STUDY SCHEDULE

In order to increase data quality, the assessments for an individual participant will be administered by the same researcher. It is important to note that consent, scales, and experiments will all take place in a private room. Any phone calls will take place in a private lab environment as well.

5.1 SCREENING

The phone screening allows researchers to screen out participants based on self-report responses and for potential participants to become familiar with the study schedule, including procedures. During the telephone screening, researchers will provide a brief background about TMS. The timeline of visits will be explained, including the number of visits and the time commitment required. The participant will be informed of compensation, both amount and payment schedule. The participant will be asked if they have any questions. Once all questions have been answered, the participant will be asked if he/she is still interested in participating in the study. If yes, the researcher will ask if the participant will provide verbal consent to begin the initial phone screening which will determine eligibility for the stimulation session. *A telephone script, which includes the screening questions, is provided in Appendix G.* If the participant meets initial criteria with these two assessments, the stimulation session will be scheduled and a reminder call or email will be given at least 24 hours before the stimulation session.

5.2 STIMULATION SESSIONS

Participants will undergo four sessions: one screening, one baseline, and two active sessions. During all four sessions, participants will be guided through the consent form. To ensure that all aspects of the research are understood, participants may be asked a series of questions about the research they are about to take part in (*Appendix E*). Once it is clear that the participant understands the consent form they may sign the form.

Session 1: Screening

- In this initial session, participants will be explained the procedure and reminded of their expectations and rights (informed consent). After obtaining consent, a pregnancy screening will be administered. Following this the participant will practice and perform cognitive control task. Participants have a self-paced break between blocks of the task.
- Participant will receive \$20 in compensation

Session 2: Baseline

- The following questionnaires will be administered during the session or will be completed remotely by the participant through an online survey weblink before the session - These measures are listed below under "self-report measures"
- Preparation - The EEG net will be applied. Resting state EEG – Participant will be asked to relax with eyes open and eyes-closed while EEG is collected simultaneously. Following this the participant will practice and perform cognitive control task. Motor thresholding using single pulse TMS for use in future sessions (performed once for each participant, either on Baseline or Stimulation 1 day). Electrodes and net will be removed and participant can wash their hair and face. Participant will receive \$30 in compensation

CONFIDENTIAL

Session 3 and 4: Stimulation 1 and 2

- The procedure for these sessions will follow the same timeline as the second, with the exclusion of informed consent, questionnaires. Motor threshold may be performed on Stimulation 1 day if it was not done during the Baseline session.
- Before practice and performance of the cognitive control task, the TMS coil will be positioned over the targeted region. During performance of the task, stimulation will be delivered on every trial. At the end of the session, participants will receive \$40, and \$60 in compensation for sessions 3, and 4, respectively.

6 STUDY PROCEDURES/EVALUATIONS

6.1 SELF-REPORT MEASURES

Study coordinator will use a standard questionnaire to screen TMS candidates. The following questions include the standard contraindications for TMS research.

1. Do you have epilepsy or have you ever had a convulsion or a seizure?
2. Have you ever had a fainting spell or syncope? If yes, please describe in which occasion(s)
3. Have you ever had severe (i.e., followed by loss of consciousness) head trauma?
4. Do you have any hearing problems or ringing in your ears?
5. Are you pregnant or is there any chance that you might be?
6. Do you have metal in the brain/skull (except titanium)? (e.g. splint, fragments, clips, etc.)
7. Do you have cochlear implants?
8. Do you have an implanted neurostimulator? (e.g., DBS, epidural/subdural, VNS)
9. Do you have a cardiac pacemaker or intracardiac lines or metal in your body?
10. Do you have a medication infusion device?
11. Are you taking any medications? (Please list)
12. Did you ever have a surgical procedure to your spinal cord?
13. Do you have spinal or ventricular derivations?
14. Did you ever undergo TMS in the past?

Affirmative answers to one or more of questions 1–13 do not represent absolute contraindications to TMS, but the risk/benefit ratio should be carefully balanced by study coordinator.

In addition, several self-report measures will be collected throughout this study. These measures are listed below and can be found in the attached documents.

- A. THE STATE-TRAIT ANXIETY INVENTORY (STAI) is a 20-item self-report assessment that assesses either temporary or chronic anxiety. For the purposes of this study, the state version will be used to measure anxiety as a result of the stress condition. The STAI is commonly used to assess both types of anxiety, and has applications in both clinical and research settings (Spielberger et al. 1983).
- B. THE BEHAVIORAL INHIBITION AND BEHAVIORAL APPROACH SYSTEM SCALES (BIS/BAS) are a set of 24 questions used to assess an individual's sensitivity to approach vs. inhibition in motivating behavior. This scale is commonly used to measure behavior and has been demonstrated to be reliable (Carver and White 1994).

- C. THE POSITIVE AND NEGATIVE AFFECT SCHEDULE (PANAS) is a 20-item self-report assessment using a 5-level Likert scale to assess the positive and negative affect of an individual over the past week. This scale has been shown to be a reliable measure of both positive and negative affect with little participantivity to demographic variables (Watson et al. 1988).
- D. THE EDINBURGH HANDEDNESS INVENTORY is a 20-item scale to assess the hand dominance of a person in everyday activities (Oldfield 1971).
- E. THE BIG FIVE PERSONALITY QUESTIONNAIRE is a 50-item self-report assessment using a 5-level Likert scale to assess five dimensions of personality (John and Srivastava 1999).
- F. REPETITIVE THINKING QUESTIONNAIRE is a 31-item self-report assessment using a 5-level Likert scale to assess levels of rumination (McEvoy et al. 2010).
- G. MONTGOMERY-ASBERG DEPRESSION RATING SCALE SELF-REPORT is a 9-item self-report assessment using a 7-level Likert scale to assess level of depression (Montgomery and Asberg 1979)
- H. MAGICAL IDEATION SCALE is a 30-item self-report assessment using a 5-level Likert scale to assess traits of schizotypy (Eckblad and Chapman 1983).

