3.2 EXCLUSION CRITERIA

A potential participant who meets any of the following criteria will be excluded from participation in the study:

- ADHD (currently under treatment)
- Neurological disorders and conditions, including, but not limited to:
 - History of epilepsy
 - Seizures (except childhood febrile seizures)
 - Dementia
 - History of stroke
 - Parkinson's disease
 - Multiple sclerosis
 - Cerebral aneurysm
 - Brain tumors
- Medical or neurological illness or treatment for a medical disorder that could interfere with study participation (e.g., unstable cardiac disease, HIV/AIDS, malignancy, liver or renal impairment)
- Prior brain surgery
- Any brain devices/implants, including cochlear implants and aneurysm clips
- History of current traumatic brain injury
- (For females) Pregnancy or breast feeding
- Anything that, in the opinion of the investigator, would place the participant at increased risk or preclude the participant's full compliance with or completion of the study

Justifications for any exclusions based on race, gender, or ethnicity: There are no exclusion criteria based on race, gender, or ethnicity. However, non-English speaking individuals are excluded because the ability to accurately and completely communicate study information, answer questions about the study, and obtain consent are necessary.

Justification for excluding women or women who become pregnant: Pregnant participants will be excluded despite the fact that theoretical risk to mother or fetus is exceedingly small, since no safety data for pregnancy is known to exist for TMS studies. Female participants will be asked if there is a possibility that they are pregnant at every stimulation session. If the participant says yes or is unsure, then we will verify pregnancy status via a urine pregnancy test. Only upon a verbal confirmation that pregnancy is not possible or a negative finding will we proceed with the experiment.

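### Section 6.1 leaves yes answers on seizures and brain implants to the coordinator's judgement, although section 3.2 makes these conditions mandatory exclusions

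*Combined protocol and SAP*

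**What the plan says.** Section 6.1 presents the question list as this study's screening tool: "Study coordinator will use a standard questionnaire to screen TMS candidates". There are 14 questions. Of a yes to any of the first 13, the section says that such answers "do not represent absolute contraindications to TMS, but the risk/benefit ratio should be carefully balanced by study coordinator". No question is carved out and section 3.2 is not mentioned.

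The questions include:

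- Question 1: "Do you have epilepsy or have you ever had a convulsion or a seizure"
- Question 7: "Do you have cochlear implants"
- Question 8: "Do you have an implanted neurostimulator? (e.g., DBS, epidural/subdural, VNS"

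Question 6 asks about metal in the brain or skull other than titanium, and gives clips as one example.

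Section 3.2 is categorical: "A potential participant who meets any of the following criteria will be excluded from participation in the study". Its list includes "History of epilepsy" and "Seizures (except childhood febrile seizures", the latter excepting only the febrile childhood type. It also excludes any brain device or implant, and names cochlear implants and aneurysm clips.

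**The concern.** For the same facts about the same person, one section prescribes exclusion and the other prescribes a judgement by a named member of staff. A coordinator working from 6.1 alone could treat a past non-febrile seizure or a cochlear implant as something to weigh.

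What is at stake is participant safety. Section 8.3 gives screening and exclusion of people with neurological conditions as the way the risk of epileptic discharge is kept low, and 6.1 is where the screening questions are set out. Section 9.4 shows how seriously the plan takes the event: one seizure at a visit puts the study on hold, and two stop it. A risk/benefit balance also fits poorly here, because section 8.1 says the healthy participants gain no immediate benefit. There is no direct benefit to set against a seizure or implant risk.

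**Working it through.** No formula applies. The check sets the 13 questions in 6.1 against the exclusion list in 3.2.

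| Question in 6.1 | Matching exclusion in 3.2 | Overlap |
|---|---|---|
| 7, cochlear implants | Brain devices and implants; cochlear implants named | Whole |
| 1, epilepsy, convulsion or seizure | Epilepsy; seizures, with childhood febrile seizures excepted | Part |
| 6, metal in brain or skull | Aneurysm clips named | Part: a yes for some other metal is not necessarily an exclusion |
| 8, implanted neurostimulator | Brain devices and implants | Part: covers a brain stimulator such as DBS, but not necessarily VNS |
| 5, pregnancy | Pregnancy | Overlaps, but not relied on: pregnancy has its own testing and stopping rules |
| 3, severe head trauma; 13, spinal or ventricular derivations | Traumatic brain injury; brain devices | Arguable, not relied on |
| 2, 4, 9, 10, 11, 12 | Not named | None relied on |

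**Count.** Relied on: 1 whole + 3 in part = 4. Not relied on: 1 (question 5) + 2 (questions 3 and 13) + 6 = 9. Total: 4 + 9 = 13.

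Four is a cautious count. Adding pregnancy would make it 4 + 1 = 5, and the two arguable items would make it at most 5 + 2 = 7.

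**Which section is meant to govern.** The rest of the protocol points to 3.2:

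- Section 8.3 says that people with a neurological history are screened out.
- Section 9.3.1 (reasons for withdrawal) removes anyone found to meet an exclusion criterion, including one missed at entry.
- Section 9.1 requires the approved IRB application to be followed throughout.
- Appendix A has eligibility assessed twice, at the telephone interview and at Session 1. Under the schedule in 5.2 the first TMS comes later, with motor thresholding at Session 2 or Session 3.

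**Who applies the rule.** Section 12.4 gives the eligibility review to the study coordinator and research assistants. The person whom 6.1 asks to weigh a yes answer is therefore among those who apply 3.2.

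**The case against.** The strongest reply is that both statements can be true. A condition may fall short of an absolute contraindication to TMS in general and still bar someone from this trial. Section 6.1 calls the questionnaire standard and nowhere permits enrolment of a person who meets a 3.2 criterion, so a coordinator who applies both sections will exclude that person. The sentence is also right for many yes answers: a childhood febrile seizure triggers question 1, yet 3.2 allows it. The safeguards in 8.3, 9.1, 9.3.1 and Appendix A would catch an error. The telephone script in Appendix G, which section 5.1 says contains the screening questions, is not in the text reviewed and may already be correct. Finally, moving the remaining judgement to the investigator is not needed to remove the conflict, and 12.4 already delegates eligibility review to the coordinator.

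Much of this stands. It shows that 3.2 is the intended rule, that three of the four overlaps are partial, and that nobody is shown to be at risk in practice. It does not remove the conflict. The sentence sits at this study's screening step, names a decision-maker and prescribes an action, so it reads as more than a background remark. A correct Appendix G would leave 6.1 and 3.2 still disagreeing. On the decision-maker, the last bullet of 3.2 already leaves discretionary exclusion to the investigator's opinion, so the proposed change follows the plan's own rule.

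**Conclusion.** The concern holds. As worded, 6.1 conflicts with 3.2 for four of the 13 questions, one wholly and three in part. It should be fixed, as a participant-safety wording correction. It has no bearing on any endpoint, analysis, power or sample size, and the number of people affected cannot be estimated from the documents.

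The conclusion rests on two readings: that the 6.1 sentence is an instruction for this study's screening, and that a brain stimulator such as DBS counts as a brain device under 3.2. The point that both eligibility checks precede the first TMS assumes the 5.2 schedule. Section 2.2 instead places motor thresholding in the first session, and section 6.2 speaks of stimulation at all four sessions.

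**What to change.** Replace the 6.1 sentence with wording to this effect:

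> Any answer showing that a section 3.2 criterion is met excludes the person. A yes answer that 3.2 does not cover (for example childhood febrile seizure, syncope, hearing problems or medications) is referred to the investigator, who decides on the balance of risk and benefit.

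The coordinator would still ask the questions and apply the 3.2 list, so the delegation in 12.4 can stay; a short note there that residual yes answers go to the investigator would keep the two sections aligned. Check that the Appendix G script says the same.

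The cost is a wording amendment to one sentence, plus that check. Nobody whom 3.2 allows is newly excluded by rule.

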6.2 SPECIAL ASSAYS OR PROCEDURES

Each participant will receive stimulation on all four sessions, separated by a week. The baseline session will involve single pulse TMS for calculating the motor threshold. The other three sessions will involve train of rhythmic TMS during performance of a cognitive control task. For stimulation day, the rhythmic TMS trains are delivered on every trial of the task (there are 600 trials per session). Each train of TMS consists of 5 pulses. There will be a total of 2400 pulses delivered per session. Each TMS train will be separated by a minimum of 5 seconds. There are three possible trains: alpha frequency with a 100 milliseconds inter-pulse interval, theta frequency with a 200 milliseconds inter-pulse interval, and arrhythmic with a variable inter-pulse interval (not to exceed a minimum of 20 milliseconds inter-pulse interval). The inter-pulse interval, inter-train interval, number of trains, and TMS intensity are all under the safety guidelines set forth by Rossi et al. 2009 and is typical for experiments that deliver online TMS (Hanslmayr et al. 2014; Albouy et al. 2017).

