2.2 DOSE RATIONALE

TMS is a safe, non-invasive, widely-used tool that applies focal electric fields to the brain using magnetic coils placed on the scalp (Rossi et al. 2009). On the first session of the study, participants will receive a motor thresholding procedure in which electrodes are attached to the first dorsal interosseous muscle of the right hand. The contralateral motor cortex will be targeted by single pulses of TMS until a motor evoked potential (MEP) is generated: defined as a near-instantaneous increase muscle activity greater than 200 microvolts. Next, the intensity of single pulse TMS will be lowered until an MEP is generated on five out of ten pulses. This is defined as the participant's motor threshold (Rossi et al. 2009). For the subsequent stimulation days, participants will receive TMS at 120% of their motor threshold. Participants will receive trains of 5 pulses at 5 hertz, 10 hertz, or arrhythmic randomized pulse intervals not to exceed an inter-pulse-interval of 20 milliseconds. Between every train will be at least 5 seconds. An inter-train-interval of 5 seconds or greater allows for any residual effects of stimulation to return to baseline. This intensity, inter-pulse-interval, and inter-train-interval is well within the safety guidelines set forth for repetitive TMS (Wassermann, 1998; Rossi et al., 2009) and has been used in similar paradigms as the one described here (Thut et al. 2011; Hanslmayr et al. 2014; Albouy et al. 2017). EEG will be collected using the Geodesic 400 system (EGI INC., Eugene, OR, USA). Collecting simultaneous EEG and TMS does not pose any additional risk over TMS on its own. EEG does not involve brain stimulation and is used purely for neuroimaging (minimal risk).

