4 BASIC STUDY DESIGN

This study is a pilot, four-session study with TMS and EEG to understand the neural oscillatory basis of cognitive control. Participants will perform a cognitive control task in which a retro-cue is used to distinguish between relevant and irrelevant lateralized stimuli that need to be accurately recalled for testing in each trial. The rhythmic TMS manipulation targets the previously localized EEG frequencies and previously localized regions of the brain from MEG (Wallis et al., 2015). The frequencies of stimulation will be theta (5 hertz), alpha (10 hertz), and arrhythmic. The regions of stimulation will be anterior-MFG, inferior-IPS. The study consists of an initial screening session, a baseline session, and two counterbalanced stimulation sessions with TMS delivered during task performance. During the initial screening session, participants will learn and perform the cognitive control task at varying levels of difficulty in order to titrate their performance accuracy. During the baseline session, participants will perform the titrated cognitive control task while EEG is recorded. The motor threshold (MT) for each participant will also be calculated either on this day or during the Stimulation 1 session. MT is calculated by placing the TMS coil at a 45-degree angle from the midline along the central sulcus (just above the ears). An electrode is attached to the contralateral first dorsal interosseous muscle. Then the primary motor cortex is stimulated with single pulse TMS until a motor evoked potential (MEP) is generated in the contralateral hand muscle, defined as a near-instantaneous increase in electrical activity above 200 microvolts. Then the intensity of TMS is lowered until an MEP is evoked on five out of ten pulses. Additionally, visible hand twitches may be used as instead of visual twitches to determine MT. The MT allows for TMS to be calibrated to the particular sensitivity level of the individual participant's brain. On the subsequent TMS session we will stimulate at 110% of MT. We ensure that TMS is driving neural activity but that this activity is within the range of endogenous activity and hence is at an appropriately safety level according to guidelines established for TMS (Rossi et al. 2009). On the third and fourth session (Stimulation 1 and Stimulation 2) the anterior-MFG and inferior-IPS is targeted by rhythmic TMS during performance of the cognitive control task. The sequence of TMS targets will be randomized and counterbalanced across participants. However, it is not possible to double-blind the study because the location of the TMS coil needs to be aligned to the targeted brain region with neuro-navigation software (Localite, Sankt Augustin, Germany). In other words, the region targeted by TMS is necessarily visible to the experimenter for accurate targeting. The study will be single blinded as the participant will not know the anatomical differences between the targeted regions and the position on the scalp differs by only a few centimeters between each site. Critically, the manipulation of interest is the frequency of stimulation. On each trial, the frequency will be randomly selected, counter-balanced, and inter-mixed. The effects of rhythmic TMS do not last for more than a few cycles beyond stimulation itself (Thut et al. 2011; Hanslmayr et al. 2014; Albouy et al. 2017). Therefore, the experimental design randomly intermixes the frequency of stimulation within every task block. The critical analysis is the within participant comparison of frequency specific TMS effects for a single site. The sequence order of target sites will have no impact because all analyses will be run as a difference from our active control (arrhythmic TMS) from within the same session. In addition, a brief resting-state EEG recording will be collected at the beginning of the

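### Section 6.2's pulse total (2400) contradicts its own inputs (600 trials × 5 pulses = 3000), and intensity is 120% of motor threshold in section 2.2 but 110% in section 4

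*Combined protocol and SAP*

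**What the plan says.** **Pulse count.** Section 6.2 says that "the rhythmic TMS trains are delivered on every trial of the task", and goes on: "there are 600 trials per session). Each train of TMS consists of 5 pulses. There will be a total of 2400 pulses". Two other sections repeat the inputs. Section 2.2 has "Participants will receive trains of 5 pulses at 5 hertz, 10 hertz, or arrhythmic randomized pulse intervals", and section 5.2 has "During performance of the task, stimulation will be delivered on every trial". Section 11.1 adds that the arrhythmic control has the same number of pulses and the same duration as the rhythmic trains.

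**Intensity.** Section 2.2 says that on the stimulation days after thresholding "participants will receive TMS at 120% of their motor threshold", and adds: "This intensity, inter-pulse-interval, and inter-train-interval is well within the safety guidelines set forth for repetitive TMS". Section 4 says: "On the subsequent TMS session we will stimulate at 110% of MT". Its next sentence argues that the stimulation "is at an appropriately safety level according to guidelines established for TMS". Section 6.2 also places the number of trains and the intensity under the safety guidelines, but gives no intensity value.

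**Task length.** Section 6.5.1 describes 10 blocks of 20 to 30 trials and does not say which sessions this applies to.

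**The concern.** Intensity and the number of pulses define what each participant receives. The protocol sets two intensities for the same sessions, and its one stated pulse total disagrees with the sentences beside it. Both intensities cannot be followed, so an operator cannot set the stimulator from the protocol alone.

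Two things are at stake. The first is the safety argument: sections 2.2, 4 and 6.2 each give an assurance, and these do not rest on one set of figures. The participants are healthy volunteers who, by section 8.1, gain no immediate benefit, and section 8.2 bases part of its physical-risk argument on individually calibrated intensity. The second is interpretation: the protocol does not fix the exposure to which a reported effect belongs.

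**Working it through.** **Inputs**

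| Quantity | Value | Where |
|---|---|---|
| Trials per stimulation session | 600 | 6.2 |
| Trials with a train | all | 5.2, 6.2 |
| Pulses per train | 5 | 2.2, 6.2 |
| Arrhythmic trains | same pulse count as rhythmic | 11.1 |
| Stated pulses per session | 2400 | 6.2 |
| Stimulation sessions | 2 | 4, 5.2, Appendix A |
| Intensity (% of motor threshold) | 120; 110 | 2.2; 4 |

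**Step 1: try to reproduce 2400.** Pulses per session = trials × trains per trial × pulses per train = 600 × 1 × 5 = 3000. The stated figure does not reproduce. The difference is 3000 − 2400 = 600, and 3000 / 2400 = 1.25.

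**Step 2: look for a reading that gives 2400.**

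- Fewer stimulated trials: 2400 / 5 = 480, leaving 120 of the 600 without a train. Sections 5.2 and 6.2 both rule this out.
- Shorter trains: 2400 / 600 = 4 pulses. Sections 2.2 and 6.2 both say 5.
- Shorter arrhythmic trains only: section 11.1 rules this out.
- Rhythmic trains only, assuming they make up two thirds of trials: 400 × 5 = 2000.
- Trial count from section 6.5.1: 10 × 20 = 200 to 10 × 30 = 300 trials, so 1000 to 1500 pulses.

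None of these yields 2400 from figures the protocol states.

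**Step 3: total over two sessions.** 2 × 3000 = 6000 against 2 × 2400 = 4800, a difference of 1200 pulses per participant.

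**Step 4: intensity.** 120 / 110 = 1.09. Both statements concern stimulation after thresholding, and no text assigns different intensities to different sessions.

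**Step 5: trial count, conditional.** If section 6.5.1 governs the stimulation sessions, 200 to 300 trials conflicts with 600. At 20 to 30 trials per block, 600 trials needs 600 / 30 = 20 to 600 / 20 = 30 blocks, not 10. For this reason 3000 is the product of the stated inputs and is not offered as the correct total.

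**Two lesser points in the same passages.** The 20 ms arrhythmic interval reads as an upper limit in section 2.2 and as a minimum in section 6.2. Read as an upper limit, a 5-pulse train would span at most 4 × 20 = 80 ms. The 10 Hz train spans 4 × 100 = 400 ms and the 5 Hz train 4 × 200 = 800 ms, so that reading also conflicts with the matched duration in section 11.1. Separately, section 6.2 counts three rhythmic-TMS sessions where sections 4 and 5.2 and Appendix A have two.

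**The case against.** The arithmetic and the clash of intensities are not in dispute. The case on the other side concerns weight and scope.

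- **The safety statements do not cite a pulse total.** This is correct. Section 2.2 refers to intensity and the two intervals, section 6.2 to those plus the number of trains, and section 4 to the level of activity. If the slip lies in pulses per train, the number of trains stays at 600. The intensity conflict alone still unsettles all three statements, and the number of trains is in doubt on the 480-trial reading.
- **Only one pulse total is printed; 3000 is a derived product.** This is also correct, but the product follows directly from the protocol's own inputs and is not put forward as the right value.
- **Section 4 argues from activity level and does not name the percentage.** Its sentence directly follows the 110% statement and fairly covers it, though section 2.2 is the plainer case.
- **The key contrast is within session, against arrhythmic TMS, and survives any reconciled value.** This stands, and no bias is alleged. A later report might state the delivered parameters, but the protocol would still not have fixed them.
- **Three sessions instead of two would change cumulative exposure by half, so calling it minor is inconsistent.** The size is right (3 / 2 = 1.5). It is treated as wording because three other places agree on two, but it still has to be aligned.
- **The pulse total alone is a lesser correction than the intensity.** This is a fair ordering: the two intensities are the more operational conflict.

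Section 9.1 has staff follow the approved IRB application, which is not among the documents. It may hold a single value, but that would not make the protocol text consistent.

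**Conclusion.** The concern holds and must be fixed. Section 6.2's inputs give 3000 pulses per session against a stated 2400 (25% higher), or 6000 against 4800 over two sessions. Sections 2.2 and 4 set intensities that differ by a ratio of 1.09, with nothing to reconcile them. The trial-count conflict with section 6.5.1 (200 to 300 against 600) applies only if that section covers the stimulation sessions.

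The finding is limited to the protocol text. Whether any of these exposures meets the cited guidelines cannot be checked from the documents, and no breach is claimed. The planned 48 participants and the analysis are not questioned on this point.

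**What to change.** Reconcile the following; this review does not choose any value.

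1. Section 6.2 internally (trials, pulses per train, total pulses) and with sections 2.2 and 5.2.
2. Section 2.2 with section 4 on intensity, and give the agreed value where section 6.2 refers to intensity.
3. Section 6.5.1: name the sessions to which the 10 blocks of 20 to 30 trials apply and, if they include the stimulation sessions, reconcile with section 6.2.
4. Derive the pulse total from the agreed inputs, showing the multiplication, and recheck the safety statements in sections 2.2, 4 and 6.2 against that one set.
5. In the same amendment, align the 20 ms interval (sections 2.2, 6.2 and 11.1) and the number of rhythmic-TMS sessions (section 6.2 with sections 4 and 5.2 and Appendix A).

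The cost is amendment wording plus the recheck of the safety statements. It needs no new data and leaves the sample size and the analysis unchanged.
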